### ***8.2.2 Qualitative analysis***

All qualitative interviews will be digitally recorded, transcribed, and simultaneously translated verbatim from Nyanja or bemba into English and then coded using *Atlas.ti*. Two research team members will conduct thematic analysis, reading and coding the data iteratively. We will first use a set of agreed upon deductive codes based on the domains addressed, followed by discussion and agreement on inductive codes that capture unanticipated and deeper analytic concepts. We will then identify and summarize key themes, with matrices for data reduction and analysis. We will organize findings as applicable, with attention to how our findings inform program development across key actors and institutions. Analyses will focus upon

changes in patient and CHW perceptions of HIV care as a result of CHW follow-up , as well as triangulate perceptions of the feasibility and acceptability of intervention components across patients, caregivers, CHWs, and facility HCWs. Attention will be paid to potential determinants (patient-level, community-level, structural, facility-based) of pilot outcomes, with consideration for modifications toward scale-up. Weekly discussions and simultaneous coding of a subset of transcripts will ensure high interrater reliability throughout; themes and findings will also be vetted through meetings with the fieldwork team. Our Key Personnel feature two Co-Investigators with extensive qualitative experience ([name], [name]).

## **9. Ethical Considerations**

### **9.1 Permission to Conduct Research at UTH**

Prior to seeking IRB approval, we will present this protocol to the UTH and Levy Head of Department and request permission to conduct this study at UTH. See appendices for letters of permission.

### **9.2 Institutional Review Board (IRB) Review and Informed Consent**

This protocol, and any subsequent modifications, will be reviewed and approved by the IRB at the University of Zambia Biomedical Research Ethics Committee (UNZABREC) of the University Teaching Hospital in Lusaka, Zambia before the commencement of the study, as well as the National Health Research Authority (NHRA). This protocol will also be reviewed by the IRB at the University of Maryland Baltimore.

### **9.3 Potential risks and benefits**

#### **9.3.1 Potential risks**

There are no more than minimal risks to participation in this study for all participants. Patients and caretakers may be uncomfortable with some of the questions posed to them in one-on-one interviews. The researcher will remind the participant that they do not have to answer any questions that make them feel uncomfortable. Loss of confidentiality is another potential risk; this is minimal and will be minimized by use of unique patient codes and de-identified data.

#### **9.3.2 Potential benefits**

There are no known direct benefits for participants in this assessment. We hope that the assessment will serve to inform and improve service provision and that participants will be pleased to know they have contributed to that effort. This information is useful on a societal level for advancing our understanding of the treatment of HIV in a resource-limited setting.

#### **9.3.3 Risk to benefit ratio and minimization of risks**

The knowledge gained from this study will be important as an addition to a very limited body of literature about post hospitalization outcomes among PLHIV in sub-Saharan Africa.

### **9.4 Voluntary participation**

During recruitment and implementation of IDIs, we will counsel participants that their participation is voluntary and regardless of the data they provide, their position with MoH, UTH, etc. will not be impacted in any way. Transcripts will be stripped of identifying information. We will approach patients who are eligible to participate in a discrete manner to maintain confidentiality. We are aware that private space is minimal in AMEU and the inpatient units and our staff will be coached on how to discuss sensitive issues in the most discrete ways possible to avoid inadvertent disclosure. If possible, a private space will be used for consenting and collection of data. When interviewees are conducted away from the hospital either at home or any other space, they will be conducted with consultation with the patient.

Potential participants will be counseled that they can refuse to participate in the study and still receive HIV care at the treatment site. Participants will be free to not answer questions

that they deem too personal during the study. Providers will be highly trained and will receive specific training in human subjects research. The study staff obtaining consent and collecting data will be highly trained in human subjects and responsible conduct of research and will have the appropriate certifications (e.g., NIH).

### **9.5 Informed consent**

Informed consent procedures will follow international standards. The consent form will be available in English, Nyanja, and Bemba; consent will occur in the language (among the three) chosen by the participant. If the participant is not literate in one of the three languages, an independent witness (either family member, friend, or clinic staff not working on the study) who is literate in the chosen language will be present and will participate in the consenting process. Study procedures will allow for potential participants to take time (potentially weeks to months if desired) to make a decision about whether or not to participate and a follow-up appointments in the days and weeks after the initial meeting can be scheduled, if desired. The participants will be encouraged to ask questions throughout the consent process and also throughout their entire participation in the study.

### **9.6 Participant confidentiality**

Throughout the study, we will maintain strict participant confidentiality in various ways. We will collect data using an ID number that is only linkable to the patient's name, phone number, and address using a linkage file. Files will be maintained in a locked filing cabinet in a locked office and the linkage file will be locked separately. Only a member of the study team will keep the keys and be able to open the file cabinets containing participant records. Access to the files will be restricted to members of the study team. If necessary, the IRB, MoH, or other regulatory body will be granted access to study files. At the end of the study, linkage files and personal identifying information will be destroyed, leaving only de-identified data for ongoing analysis and dissemination.

### **9.7 Participant withdrawal**

Participants will be allowed to withdraw from the study at any time and for any reason and without stating a reason. Participants will be provided with the PI and other study team members' phone numbers and if the participant informs the study team of her/his wish to leave the study, that wish will be honored. Participant data and records would be destroyed at that point and the ethics committee would be informed of the withdrawal.

### **9.8 Participant treatment**

Participants will receive clinical care and treatment according to the MoH guidelines on HIV management and per the standards of care. A study team member will be available to participants by phone at all times and patients who require hospitalization after discharge or additional medical attention will be referred to the appropriate public sector facility.

## 10. Study Time Frame

Following IRB approval, we will organize a stakeholder meeting to explain the research and the purpose. We will then begin data collection using IDIs, followed by data analysis. Following completion of data analysis, the results will be disseminated through a variety of channels, including through educational programs at UTH, conference presentations, and publication in a peer-reviewed journal.

Timeline for Major Activities	2022		2023				2024			
	Q3	Q4	Q1	Q1	Q3	Q4	Q1	Q2	Q3	Q4
IRB Approvals		X								
Stakeholder meetings	X									
Pre-implementation data collection			X	X	X					
CHW intervention implementation					X					
Post implementation data collection					X	X				
Data collection: IDIs					X	X				
Data analysis						X	X	X		
Local dissemination of findings							X	X		
Conference presentation								X	X	
Manuscript development & publication									X	X

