## 1. Protocol Synopsis

Full Title	Re-engagement at Discharge 2: Improving post-hospital outcomes for adults with HIV in Zambia (ReCharge 2)
Clinical Trial Phase	N/A
Principal Investigators	[name], MPH [name]
Co- Investigators	[name], PhD [name], PhD, MMed, MSc. [name] [name] [name], MMed [name] [name] [name], MMed [name], MMed [name], RNHNP
Sample Size	N = 100
Study Population	Eligible patients living with HIV hospitalized at University Teaching Hospital or Levy Mwanawasa Hospital, Lusaka, Zambia
Accrual Period	1/1/2023-6/1/2024
Study Design	Single Arm Pre/Post Pilot Study
Study Duration	2 years
Study Agent/ Intervention Description	Community health worker (CHW) follow-up after discharge from hospital
Primary Objective	1. To assess the feasibility and acceptability of CHW follow-up following hospitalization
Secondary Objectives	1. To estimate the potential impact of the pilot program on the proportion who are alive and virally suppressed at 6 months post-discharge 2. To understand implementation factors related to pilot program
Exploratory Objectives	1. To investigate barriers and facilitators to ART adherence for PLHIV following hospitalization 2. To investigate barriers and facilitators to community-based support for PLHIV following hospitalization
Primary Endpoints	1. The proportion of discharged patients who are successfully visited after discharge. 2. The proportion of discharge follow-up visits by a CHW that are comprehensive 3. The proportion of initial post-discharge visits to the ART clinic that are attended by the participant's CHW supporter.
Secondary Endpoints	1. HIV viral load at 6 months post-discharge. 2. Mortality within 6 months of discharge. 3. Retention in HIV care after discharge defined by no gap of >28 days off ART from discharge date to 6 months post-discharge date. 4. ART clinic visit within 1 month of discharge 5. Transition back to ART care at original (pre-admission) clinic

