### 5.2.2 Historical control data:

To make inferences around possible impact, which will inform the sample size of a fully-powered future trial, before implementation of the intervention, we will collect historical control data on the outcomes of interest. We acknowledge that our comparison of trial outcomes to those from historical controls will be prone to time trends in patient outcomes and in clinical practices, which could make the intervention appear to have spurious effects. To minimize this bias, we will collect historical control data on discharged patients just prior to implementing the intervention. These will be participants with the same inclusion/exclusion criteria as intervention patients and recruited in the same way.

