#### **5.2.4 Quantitative outcomes:**

Our primary effectiveness outcome will be alive and virally suppressed at 6 months after hospital discharge. Patients who either pass away or have a viral load >60 copies/ml will be considered failures. Patients who are alive but have unknown VL will also be considered failures. Those who transfer care outside of Lusaka District (we expect this to be 2-3%, based on a prior study) will be censored. We will also evaluate numerous secondary outcomes, including retention on ART, defined as possession of ARVs within 30 days of the 6-month post-discharge time point, consistent with PEPFAR TX\_CURR definition. We will also assess ARV adherence (based on medication possession ratio), number of visits attended, and the rate of hospital re-admission.

To ascertain these outcomes, our research assistant will contact the client each month post-discharge to check vital status (alive versus dead) and whereabouts. At 6 months after discharge, we will confirm the location of last HIV care and arrange for patient to have HIV VL, either back at the hospital or at their local clinic. The team will extract electronic medical records from the clinic including visit, pharmacy, and laboratory data, including HIV viral load results. Transfers within Lusaka (where there are 30+ ART clinics) are common and this approach will allow us to have complete end-line data for most clients, including historical controls and pilot participants.

We will also collect implementation outcome data during the trial, such as proportion of trial participants who do not receive any CHW services, the number and type (phone calls, home visits, meetings at the facility) of interactions between participants and CHWs. Semi-structured interviews with a subset of patients will be done to check acceptability of the intervention.

To begin to understand and anticipate meaningful patterns in our pilot data, we will also collect socio-demographics and socio-economic data on patients and their households, as well as capturing extent and severity of co-morbidities. We will include the following measures, captured at the following time points:

At enrollment/in hospital:

- Education (highest completed grade attained) for patient and primary caregiver
- Age, marital status, number of children
- Relationship to household head
- Religion and religiosity (affiliation, frequency of church attendance (weekly))

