## 6.4 Participant recruitment

### 1. Hospitalized patients living with HIV being discharged home

Our team will integrate with the inpatient teams at the Internal medicine units at study sites. We will solicit from the teams patients who may be eligible to enroll. A research team member will assess criteria and if eligible the patient will need to provide written informed consent to enroll. We expect that 30-40% of adults admitted to Internal medicine have HIV, and among them, about 30% will meet criteria to participate. We expect it will take 3-4 months to enroll the needed sample size.

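### The Section 10 chart closes post-implementation data collection before essentially any pilot patient reaches the 6-month endpoint, and it conflicts with the stated accrual period and control timing

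*Combined protocol and SAP*

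**What the plan says.** Section 10 lays out activities over ten quarters, Q3 2022 to Q4 2024. The second 2023 column is labelled Q1 again but is plainly Q2. The relevant rows are:

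- "Pre-implementation data collection": Q1 to Q3 2023
- "CHW intervention implementation": Q3 2023 only
- "Post implementation data collection": Q3 and Q4 2023
- In-depth interviews: Q3 and Q4 2023
- Data analysis: Q4 2023 to Q2 2024
- Local dissemination: Q1 and Q2 2024

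Section 5.2.4 sets the endpoint: "Our primary effectiveness outcome will be alive and virally suppressed at 6 months after hospital discharge". It is collected actively: "At 6 months after discharge, we will confirm the location of last HIV care and arrange for patient to have HIV VL". Section 5.3.2 places the second patient interview at the six-month follow-up.

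On recruitment, the synopsis gives the accrual period as "1/1/2023-6/1/2024", and Section 6.2 gives the same window for admissions, ending on 1 June 2024. Section 6.4 states: "We expect it will take 3-4 months to enroll the needed sample size". On controls, Section 5.2.2 states: "we will collect historical control data on discharged patients just prior to implementing the intervention".

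**The concern.** A 6-month endpoint that needs a blood draw can be obtained only if data collection is still open six months after discharge. The package starts at discharge with the discharge card (Section 5.1), so no pilot discharge can precede the implementation quarter. Yet the chart allows only that quarter and the next before collection ends.

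The main use of the comparison is to inform the size of a future trial (Section 5.2.2). If the chart were followed, 6-month viral loads would be missing for nearly all pilot patients, and Section 5.2.4 counts a living patient with an unknown viral load as a failure. That would lower the pilot group's success proportion against any controls who had complete follow-up. The second patient interviews would be cut off in the same way, and they inform acceptability, which is part of the primary objective.

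The overlap with control collection matters for a different reason. Collecting controls before implementation, and close to it, is the protocol's own safeguard against time trends. Controls discharged from wards already using the card would not be unexposed.

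**Working it through.** No sample-size or power figure is involved. The check is calendar arithmetic on the quarter columns.

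**Inputs.** Implementation window: 1 July to 30 September 2023 (Section 10). Close of post-implementation collection: 31 December 2023 (Section 10). Endpoint: discharge plus 6 months (Section 5.2.4). Enrolment duration: 3 to 4 months (Section 6.4). Accrual end: 1 June 2024 (synopsis, Section 6.2).

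**Pilot group.** Endpoint date = discharge date + 6 calendar months. Follow-up at close = (31 December 2023 − discharge date) / 30.44 days.

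| Discharge | 6-month date | Follow-up at close |
|---|---|---|
| 1 July 2023 | 1 January 2024 | 183 days, 6.0 months |
| 15 August 2023 | 15 February 2024 | 138 days, 4.5 months |
| 30 September 2023 | 30 March 2024 | 92 days, 3.0 months |
| 31 October 2023 (4-month enrolment) | 30 April 2024 | 61 days, 2.0 months |

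By calendar months the earliest discharge misses the close by one day. With six months taken as 182 days, the last qualifying discharge is 31 December − 182 days = 2 July, so 2 of the 92 days in Q3 qualify. The 4-month case also runs past the single implementation quarter on the chart. A start later in Q3 widens the gap.

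**Accrual period.** 1 June 2024 + 6 months = 1 December 2024. The analysis and local dissemination rows both end in Q2 2024.

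**Controls.** To complete 6 months by 30 June 2023, the day before the implementation quarter, a control would need discharge by about 30 December 2022, before accrual opens on 1 January 2023. To complete 6 months within the control row (by 30 September 2023), discharge is needed by about the end of March 2023. Controls discharged in Q2 2023 would therefore reach month 6 only after that row ends. The control and implementation rows share Q3 2023.

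**The case against.** The strongest reply is that Section 10 is a quarter-resolution overview of major activities and not a rule for closing data collection. Section 5.2.4 is the operative text. It requires monthly contact, a viral load at 6 months, and extraction of clinic visit, pharmacy and laboratory records, and it expects this to give endline data on most patients in both groups. Nothing tells staff to stop before month 6. This stands as a limit on the consequence: a reader might infer that the 6-month outcomes cannot be observed, but the documents show only that the chart and the outcome section disagree. Even under truncation, the monthly contacts would capture deaths up to the close.

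Three further replies have force.

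- A reader might say that no pilot patient at all reaches the endpoint in time. That rests on a one-day margin and fails at 182 days. A tolerance would also help: Section 5.2.4 allows 30 days around month 6 for ART retention, though it states none for viral load. If a viral load 30 days early were accepted (an assumption), the threshold is 182 − 30 = 152 days. Discharges up to 1 August would then qualify, 32 of the 92 days, and most of the quarter would still not.
- A reader might infer that controls were contaminated. The shared Q3 mark could be follow-up of controls discharged earlier, or control collection could end and implementation begin within the quarter. The Q2 controls' results could also be extracted later from records.
- 1 June 2024 may be an overall window covering both groups. With 3 to 4 months of enrolment from Q3 2023, the last endpoints fall around March to April 2024. December 2024 is the outer limit, not the expected case.

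None of these reconciles the chart with the endpoint or with the accrual dates.

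**Conclusion.** The point holds as an inconsistency of substance: the printed schedule cannot deliver the stated effectiveness endpoint. On the chart, essentially no pilot patient reaches 6 months before collection closes on 31 December 2023. A mid-window discharge has about 4.5 months of follow-up by then, and the endpoints actually fall from about 1 January to 30 March 2024, or to about 30 April 2024 with four months of enrolment. This assumes that the marks are read as whole quarters and that pilot discharges begin no earlier than 1 July 2023. The conflict with accrual to 1 June 2024 is separate and does not depend on the one-day margin.

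Two consequences remain conditional. Missing viral loads would be counted as failures only if staff followed the chart over Section 5.2.4; no text says that a patient who has not yet reached month 6 is a failure. Contamination of controls is a risk arising from an overlap visible only at quarter resolution. The documents establish neither as something that will happen.

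**What to change.** Reconcile Section 10 with the synopsis accrual period and Sections 5.2.2, 6.2 and 6.4, then redraw the chart:

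- Extend the post-implementation collection and endline interview rows to at least 6 months after the last pilot discharge, plus a stated window for the viral load. For a Q3 2023 start with 3 to 4 months of enrolment, that means into Q1 to Q2 2024. If accrual really runs to June 2024, the rows must run into December 2024 or later; otherwise bring the accrual end date forward.
- Start the 6-month outcome analysis only after that point.
- Show control enrolment and control follow-up as separate rows. Close control enrolment at each hospital before the first discharge card or CHW enrolment there.

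No extra patients or procedures are needed. The cost is later analysis and dissemination, and possibly longer staffing for data collection; the budget in Section 12 shows only a Year 1 column. If the 2-year duration is counted from January 2023, a last endpoint on 1 December 2024 leaves about one month for the viral load window, analysis and dissemination, which favours an earlier accrual end date if the overall calendar is fixed.

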## 11. Publication plan

It is expected that the results of the study will be presented at an infectious disease conference (e.g. CROI, IDSA/ICAAC, or IAS/IAC). It is anticipated that the study will generate an abstract. We anticipate that the study will also generate a manuscript that will be submitted to an infectious disease journal such as *Journal of the International AIDS Society*, or other journals of a similar caliber. It is anticipated that a manuscript would be submitted within 6 months of completion of the final analysis of the study data.

## 12. Budget

Budget (in Kwacha)	Year 1
Personnel	
Key personnel salaries	300,000
Other staff salaries	200,000
Travel	
Local travel (Lusaka)	40,000
Other	
Participant costs (such as transport reimbursements)	20,000
Training costs (for study team and UTH staff)	40,000
Meeting costs (for sensitization and dissemination)	35,000
Miscellaneous costs (stationery, office rent, etc.)	20,000
Indirect costs	150,000
Total	800,000

## **14. Appendix 1: Patient Interview Guide**

### **IDI Interview Guide for patients, Interview 1 (~1-week post-discharge)**

#### **Background information:**

*(Objectives: Rapport building, understanding of potential sources of support, assessment of living situation and economic status, understanding of other health-related behaviors as it relates to any leisure activities) (Interests? Ways they earn a living?)*

1. Can you please tell me about yourself and the family members who live here with you?
  - a. Tell me about everyone who lives here on a regular basis with you. How are they related to you? (Possible probes: married? Kids? Ages?)
  - b. Can you talk about any other close family members who live nearby and who are important to you in your life?
  - c. Tell me a bit about how people in this household get by, what are the different kinds of work they do?
  - d. When you are feeling well, what are some of the things that you do when you have free time, or for recreation:
    - i. Possible probes: Reading, watch TV, do you take alcohol, smoke, what about others in your family?

2. *(Objective: These questions are to understand the role of stigma and whether participant perceives stigma or themselves as burden or source of shame within household/community – in case these factors have played a role in how they are cared for/care for themselves; whether/how they feel their identity as a PLHIV has had any negative impacts on their life within their community)*

Thank you. Now, if it's okay, I'd like to understand a bit more about your health. To start, would you please tell me in detail how you learned about your status? (NOTE: try to get them to tell this to you as a story, they can set the stage/scene - Age, circumstance- what year was it?)

- a. Can you talk about how you felt after learning about your status at that time? Have your feelings changed since that time and how?
- b. Have you told anyone about your status (or has anyone learned about your status without you telling them? How did they come to know about it?
  - i. How was that experience (disclosure) for you?
  - ii. Were there any changes in relationships with family over time?

3. *Objective: To understand how the participant has approached treating their HIV, different treatment regiments they may have tried prior to ART, different influences on different ways of getting treatment etc. AND to establish the context around their starting on ART, and how they got it and how they felt about it from the beginning. Also want to see if the mechanisms by which they accessed it have changed at all as this may be part of the problem.*

Thank you so much for sharing that with me. Now I'd like to understand more about your experience with caring for your health. **NOTE: Ask these items only if the person reported knowing their status before being hospitalized.**

- a. Let's start with right after you learned your status. Can you talk about how you cared for your health during that time? (*Try to figure out when this was – before/after test and treat?*)
  - b. Now let's talk about any changes more recently in how you have looked after yourself.
  - c. Let's talk in a bit more detail about ART if you don't mind.
    - i. Have you ever been on ART? Can you describe how you started to take ART? (If not already addressed above)
    - ii. Who encouraged you to start, when did you start, how did you start taking ART?
    - iii. What was your experience with taking ART? (Emotional response to taking it, physical response to taking it in the body).
    - iv. Can you talk about where and how you have accessed ART over time and whether or how this changed?
- d. **Ask all participants:** Apart from going to the clinic as a way of taking care of your health, have you tried different methods or ways of taking care of your health over time? Can you talk about these?
  - i. Can you talk about who encouraged you to take these different approaches (ART? other healing practices? Church/religious influence?)
  - ii. **If influenced by church – ask them to talk more about this** – Can you talk more about the guidance you received from your church?
  - iii. Can you also tell me a bit more about the church? (What type)
- e. Can you talk about any other health challenges you have been facing?

4. *Objective: These questions will help us to understand their perceived barriers to staying on treatment. Hope here is that some of these might be amenable to intervention with CHWs.... So we want to try to identify any of these.*

Many of us have a difficult time accessing and staying in HIV care or on treatment( **That is accessing the drugs, staying on ART without stopping**). For many, the challenges they face with staying on ART lead them to be non-adherent (not taking treatment everyday) or even stop taking it. Can you describe any experiences you have had with this?

**For these question, make that you probe on challenges by asking the participants on challenges related to accessing ART, Taking ART, Staying on ART etc.**

- a. Can you talk about any challenges you faced with taking ART?
  - i. Challenges at home/In household? Community?
  - ii. Concerns with taking it because of advice received (from family, friends, church)
  - iii. Challenges with clinic / accessing drugs? (Stigma, time, cost, distance, rude staff)
  - iv. Challenges/barriers within yourself (acceptance of status, motivation, beliefs, fears, side-effects, what others might think etc.)
- b. Now, among all of the reasons you have just mentioned, which of these reasons would you say mattered the most. What makes you say that? (rank exercise)
- c. Were you able to overcome any of these challenges? (**If yes**, can you talk about how you overcame the challenges? **If no**, what could help you to overcome these challenges?)

5. *(Objective: Understand their support system since diagnosis, changes to that system, and whether they have one or feel they have one and who primarily it consists of – Does their family support them, who in the family – did someone supporting them early on move away, leave, pass away? Etc.)*

Now I would like to understand more about the people in your life who have supported you since you learned about your status.

- a. Who would you say has helped or supported you the most? In what ways?
- b. Have the people who have cared for you/supported your health changed over time?
  - i. Can you talk about this and why was there this change, how did this affect you and your treatment/health? (PROBE to identify role of family members in the household)

**Thank you for sharing this with me. Now I'd like to ask you more about your most recent health challenges that took you to the hospital, if you don't mind.**

6. Can you talk about your most recent hospitalization, tell me about what happened?

- a. What led to your going to the hospital?
- b. How did you get there? Who helped you realize you needed to go? Who helped you to get there?
- c. Can you just let me know, quickly, about how many other times you have been admitted to the hospital in the past since you learned about your status?
  - i. Can you talk about the events that led to your hospitalization in the past?

*(Objective: Want to know about the additional concerns they may have been facing with their health that led to their hospitalization; additional questions here on social support/family support)*

7. Thinking now about the most recent time you were in the hospital - Can you talk about your experience in the hospital?

- a. What did you learn about the cause of your illness that led to your being hospitalized while you were there?
  - i. What other information was shared with you by the doctors/nurses about your medical condition?
  - ii. How did that make you feel?
- b. Can you talk about how being in the hospital made you feel?
  - i. PROBE on whether those feelings have motivated them to act or lose hope...without saying this directly!

8. Now, can you please tell me about what was the discharge process like for you?

- a. Can you talk about how you learned you were going to be discharged? (PROBE: sudden, knew a few days in advance?)
- b. How did you feel about being discharged when you were? (Early? Late? From their perception)
- c. Can you describe for me in detail everything you were advised to do following discharge?
  - i. What exactly do you remember being told to do once you left the hospital?

- ii. Did the hospital provide you with any referral to help you get connected to care?
- iii. How did you feel about the advice/instructions you were given? (Easy to understand, not feasible, helpful, unhelpful, etc.)

9. Now, let's talk about how it was after you left the hospital. How has it been since you were discharged? Can you talk about that?

- a. How have you been feeling?
- b. What has been worrying you?
- c. What is going well or getting better?
- d. Who has been helping you with your health since discharge? Can you talk about how they have been helping?

10. Now I'd like to ask you more about what you need in order to completely recover.

- a. What do you think are the things that you need in order to get better?
- b. What does your family need in order to be able to support you to get better?
- c. In addition to medical advice and treatment, what additional form of support do you need to stay/get healthy? ( e.g., Nutrition , information, psychological, financial, religious )
- d. What are all the challenges you are facing now to stay/get healthy?
  - i. With treatment, clinic, or access to healthcare
  - ii. With family or support
  - iii. With finances following hospital stay
  - iv. Within community or its expectations
  - v. Others? (Probe on those related to ART and ART use, especially cost of healthcare -transportation, labs, tests, medicines)
  - vi. What is it that you think should be done to help you overcome these challenges?
- e. What kinds of support are you receiving? And from where? Whom?

11. Thank you very much for your time. Do you have any questions or comments before we close this interview?

- a. Is there anything else that you would like us to talk about that you think is important for me to understand about your problems with your health?
- b. Do you have any additional recommendations you would like to share on whether or how CHWs, or other healthcare workers, could better serve patients after discharge to ensure they recover as best as possible?

